The trial will be carried out in accordance with International Conference on Harmonization Good Clinical Practice (ICH GCP) and the following:

- United States (US) Code of Federal Regulations (CFR) applicable to clinical studies (45 CFR Part 46, 21 CFR Part 50, 21 CFR Part 56, 21 CFR Part 312, and/or 21 CFR Part 812)

National Institutes of Health (NIH)-funded investigators and clinical trial site staff who are responsible for the conduct, management, or oversight of NIH-funded clinical trials have completed Human Subjects Protection and ICH GCP Training.

The protocol, informed consent form(s), recruitment materials, and all participant materials will be submitted to the Institutional Review Board (IRB) for review and approval. Approval of both the protocol and the consent form must be obtained before any participant is enrolled. Any amendment to the protocol will require review and approval by Exelixis and the IRB before the changes are implemented to the study. In addition, all changes to the consent form will be IRB-approved; a determination will be made regarding whether a new consent needs to be obtained from participants who provided consent, using a previously approved consent form.

ABBREVIATIONS

AE	Adverse Event
CFR	Code of Federal Regulations
CMP	Clinical Monitoring Plan
COC	Certificate of Confidentiality
CONSORT	Consolidated Standards of Reporting Trials
CR	Complete Response
CRF	Case Report Form
DCC	Data Coordinating Center
DCR	Disease Control Rate
DHHS	Department of Health and Human Services
DSMB	Data Safety Monitoring Board
DRE	Disease-Related Event
EC	Ethics Committee
eCRF	Electronic Case Report Forms
FDA	Food and Drug Administration
FDAAA	Food and Drug Administration Amendments Act of 2007
FFR	Federal Financial Report
GCP	Good Clinical Practice
GLP	Good Laboratory Practices
HIPAA	Health Insurance Portability and Accountability Act
IB	Investigator's Brochure
ICMJE	International Committee of Medical Journal Editors
IND	Investigational New Drug Application
IRB	Institutional Review Board
ISM	Independent Safety Monitor
ISO	International Organization for Standardization
ITT	Intention-To-Treat
MOP	Manual of Procedures
MSDS	Material Safety Data Sheet
MTD	Maximum Tolerated Dose
NCT	National Clinical Trial
NIH	National Institutes of Health
NIH IC	NIH Institute or Center
OHRP	Office for Human Research Protections
PI	Principal Investigator
PR	Partial Response
QA	Quality Assurance
QC	Quality Control
ORR	Overall Response Rate
RP2D	Recommended Phase 2 Dose
SAE	Serious Adverse Event

SAP	Statistical Analysis Plan
SD	Stable Disease
SMC	Safety Monitoring Committee
SOA	Schedule of Activities
SOP	Standard Operating Procedure
ULN	Upper Limit of Normal
UP	Unanticipated Problem
US	United States

1. PROTOCOL SUMMARY

1.1 SYNOPSIS

Title:**A Phase 1b/ 2 Study of Cabozantinib in Combination with Pembrolizumab in Advanced Melanoma****Study Description:**

The study aims to evaluate the safety and preliminary efficacy of the combination of cabozantinib and pembrolizumab in advanced melanoma. The phase 1b study is based on 3+3 design with fixed dose of pembrolizumab and three dose levels of cabozantinib. The phase 2 study will be conducted in two stages, with a hypothesis of improving the response rate to 55%.

Objectives:

Phase 1b: To establish the recommended phase 2 dose of cabozantinib in combination with pembrolizumab in patients with unresectable melanoma and assess the safety and tolerability of the combined treatments.

Phase 2: To evaluate the preliminary efficacy of the established dose of cabozantinib in combination with pembrolizumab as measured by best overall response rate (ORR) (complete response (CR) + partial response (PR)) with the combination of agents in patients with unresectable stage III or stage IV melanoma.

Endpoints:

Phase 1b: Combination of cabozantinib and pembrolizumab is safe to use in advanced melanoma

Primary Endpoint: Objective response rate

Secondary Endpoints: Clinical benefit (DCR and duration of DCR), time to response, progression-free survival and overall survival.

Study Population:

Adults with unresectable stage III or stage IV advanced melanoma

Phase:

1b/2

Description of Sites/Facilities

This single center study will be conducted at the Holden Comprehensive Cancer Center of the University of Iowa Hospitals and Clinics.

Enrolling Participants:

The biomarker part of the study will be decided at a later date.

Description of Study Intervention:

[figure not shown]
[figure not shown]
A combination of cabozantinib and pembrolizumab will be tested in the study. Cabozantinib will be administered in the tablet form, at three dose levels: 40, 20 and 60 mg per day. Pembrolizumab will be administered as an intravenous infusion at a fixed dose of 200 mg once every 3 weeks.

1.2 SCHEMA

Phase 1b:

Dose Level	Cabozantinib	Pembrolizumab
-1	20 mg	200 mg
0	40 mg	200 mg
1	60 mg	200 mg

Study Design

Phase 2: The target population includes patients with pathologic or cytologic evidence of melanoma, clinical stage IV or recurrent/medically inoperable disease, a ECOG performance score ≤ 2 and a life expectancy of >12 weeks, adequate hematologic, renal, and hepatic function, and measurable disease.

Patients who are taking other investigational agents, or who have uncontrolled CNS metastases or unstable medical conditions such as decompensated heart failure, unstable angina, uncontrolled hypertension or diabetes and active infections are to be excluded from this study. Treatment will begin only after patients have fully met all inclusion criteria and none of the exclusion criteria and a valid informed consent has been signed.

Subjects will receive cabozantinib, orally at the MTD dose obtained from phase 1b part of the study in combination with pembrolizumab administered IV at 200 mg once every 3 weeks. After baseline tumor evaluation, tumor assessments will be performed with interval imaging every 12 weeks starting from Week 12 until progression with a CT scan and response evaluated per RECIST 1.1. Appendix A. Progressive disease per RECIST or unacceptable toxicity will result in the subject's termination of the study drug.

Prognostic Stage Group: the eighth edition American Joint Committee on Cancer (AJCC) melanoma staging system groups patients into four prognostic stage groups. The details of prognostic group staging:

- Stage I – Stage I melanoma is limited to patients with low-risk primary melanomas (T1a, T1b, and T2a) without evidence of regional or distant metastases. Stage I is divided into stages IA and IB based upon the thickness of the primary tumor and the presence or absence of ulceration.
- Stage II – Stage II disease includes primary tumors that are at higher risk of recurrence (T2b, T3a, T3b, T4a, and T4b) but do not have any evidence of lymphatic disease or distant metastases. Stage II is divided into stage IIA, IIB, and IIC depending upon tumor thickness and the presence or absence of ulceration.
- Stage III – Stage III disease includes pathologically documented involvement of regional lymph nodes or the presence of in transit or satellite metastases (N1, N2, and N3). Patients with stage III disease are subclassified as having stage IIIA, IIIB, IIIC, or IIID disease depending upon the extent of lymphatic disease.
 - Unknown primary – Patients with isolated metastases identified in the lymph nodes, skin, or subcutaneous tissue who do not have an identifiable primary cutaneous melanoma (T0) are classified as pathologic stage III, assuming no other sites of disease are identified after an appropriate staging evaluation. Other sites of metastases from an unknown primary melanoma are classified as stage IV.
 - Stage IV – the presence of distant metastases defines stage IV disease (M1a to M1d). Central nervous system metastases (M1d) are associated with a particularly poor prognosis. There are no subgroups.

1.3 STUDY CALENDAR

Assessments	Screening 28-day window up to Day 1 of treatment ¹	Day 1 of Every ODD Cycles (1, 3, 5...) +/- 5 days	Day 1 of every EVEN cycle Cycles (2, 4, 6...) +/- 5 days	END of Treatment Visit ²	Follow Up ³ (every 3M from EOT Visit
Informed Consent ⁴	X				
Inclusion/Exclusion Criteria	X				
Medical History/ Prior Treatment ⁵	X				
Concomitant medications	X	X	X	X	
Physical Exam	X	X	X	X	
Performance Status (ECOG or KPS)	X	X	X	X	
Vital signs/Weight/Height ⁶	X	X	X	X	
Drug Toxicity Assessment ⁷	X	X	X	X	
Baseline daily stool count	X				
ECG ⁸	X ⁹	EVERY 12 weeks (Pre- Cycle 5, 9, 13, ...)		X	
ECHO- 2D/MUGA	X				
Pregnancy test ¹⁰	X				
CBC with Differential ¹¹	X	X	X	X	
Chemistries ¹²	X	X	X	X	
PT/INR and PTT ¹³	X			X	
Urinalysis and UPC	X	X	X	X	
Thyroid Function Tests ¹⁴	X		X	X	
Amylase, Lipase	X	Every 12 weeks (Pre-Cycle 5, 9, 13...)		X	
Hepatitis B and C ¹⁵	X				
Tumor Imaging- CT Chest/Abdomen/Pelvis ¹⁶	X	Every 12 weeks (Pre- Cycle 5, 9, 13...)		X	
Brain MRI ¹⁷	X				
Pill Diary/Pill Count ¹⁸		X	X	X	
Research Blood ¹⁹ Phase II only	X	At week 7 (+/- 1 week) and progression			
Archival Tissue ²⁰ Phase II only	X				
Tissue Biopsy ²¹ Phase II Part 2 only	X	At week 7 (+/- 1 week) and progression			
Cabozantinib PO		Daily	Daily		
Pembrolizumab IV (30- minute infusion)		Day 1 of each Cycle			
Survival Status					X

¹ Routine laboratory tests for screening should be performed within 14 days of cycle 1.

² End of treatment visit will be completed 30 days (+/- 7 days) from date of last dose of study drug or before another treatment starts whichever occurs first.

³ Subjects will be followed for survival and progression post treatment every 3 months x 2 years, every 6 months x 3 years and yearly until death. Every 3 months from EOT visit.

⁴ Written consent must be obtained prior to performing any protocol specific procedure. Results of a test performed as part of routine clinical management are acceptable in –lieu of a screening test if performed within the specified time frame. (e.g., within 28 days period to Cycle 1 Day 1.)

⁵ Report complete medication history for 30 days prior to the screening visit. Medical history should include history of treatment for the primary diagnosis, including prior systemic, radiation treatment and surgical treatment and best response to prior systemic treatments. Date of last prior cancer treatment must be documented.

⁶ Vital signs to include weight, temperature, pulse, respiratory rate and blood pressure. Height will be measured at screening only.

⁷ Adverse events and laboratory safety measurements will be graded per NCI CTCAE version 4.03. All adverse events, whether gradable by CTCAE or not, will also be evaluated for seriousness.

⁸ ECG must be completed within 14 days before Cycle 1 Day 1. If at any time on study, there is an increase in QTcF interval to an absolute value > 500 ms, two additional ECGs must be performed, within 30 minutes after the initial ECG (each with intervals 2 minutes apart).

⁹ Triplicate ECGs will be performed at screening only with intervals of at least 2 minutes apart. Single ECGs will be done every 12 weeks and at EOT.

¹⁰ For women of reproductive potential, a urine pregnancy test will be performed within 72 hours of the first dose of therapy. If urine pregnancy results cannot be confirmed as negative, a serum pregnancy test will be required. Pregnancy test (serum and/or urine) should be repeated if clinically indicated.

¹¹ Routine laboratory tests may be collected up to 48 hours prior to Day 1 of any Cycle.

¹² Chemistries to include: Glucose, blood urea nitrogen, creatinine, sodium, potassium, chloride, bicarbonate, calcium, total protein, albumin, serum bilirubin, alkaline phosphatase, ALT, AST, LDH, GGT, phosphorus and magnesium.

¹³ PT/INR and PTT will be collected at Screening, End of Treatment and as clinically indicated.

¹⁴ T3, Free T4, and TSH will be performed at screening, Day 1 of EVEN Cycles and EOT visit.

¹⁵ Subjects will be tested for hepatitis B and C during screening if they are considered by the investigator to be at higher risk for these infections and have not been previously tested.

¹⁶ Tumor imaging will be performed within 28 days prior to enrollments. CT Chest/Abdomen/Pelvis with contrast is required unless a patient has a clinical condition such as a severe contrast allergy or the lesions are significantly better visualized through the use of an MRI. The same imaging technique must be used in a subject throughout the study. In addition, subjects with progressive disease consider a second scan in at least 4 weeks to confirm progression and exclude the possibility of a tumor flare reaction, according to irRC guidelines, this would be at the investigator discretion. If there is an increase in tumor burden at week 12, the baseline sum of perpendicular diameters is to be reset to week 12 for subsequent assessment of response.

¹⁷ If clinically indicated.

¹⁸ Subjects should use a study pill diary (Appendix C) to record their daily dose of cabozantinib. Subjects should bring the pill diary with them each time they return for a study visit. Study pill counts will be done at the end of each cycle prior to dispensing a new supply of study medication. Reasons for discrepancies in pill counts will be documented in the subject's study binder.

¹⁹ Phase II only: 5 tubes of blood will be drawn at baseline, week 7(+/- 1 week) and at progression for future biomarker testing.

²⁰ Phase II only: An archival tissue sample of at least one tumor lesion is mandatory. If archival tissue is not available subject must agree to a new biopsy sample.

²¹ Phase II Part 2 only: An optional tumor tissue core biopsy will be performed at 7 weeks (+/- 1 week) and at time of progression. Recommend: Per PI discretion, Cabozantinib be held for 4 days prior to biopsy and restarted 7 days after biopsy provided adequate wound healing is achieved.

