4 STUDY DESIGN

4.1 OVERALL DESIGN

The study is designed as a prospective trial to evaluate the combination of cabozantinib and pembrolizumab in adult patients with advanced melanoma who did not previously receive cabozantinib. Prior use of anti-PD-1 inhibitors is allowed in the adjuvant setting provided that the last dose is longer than 6 months prior to developing metastatic disease. Pembrolizumab will be used at the recommended approved dose for this indication.

This single institution, investigator-initiated trial has two phases: a phase 1b dose escalation of cabozantinib in combination with pembrolizumab, to establish the recommended phase 2 dose for the combination. The Dose Escalation Phase will utilize a 3+3 design over 3 planned dose levels leading to the identification of aR2PD and MTD for the combination of cabozantinib and pembrolizumab.

This will be followed by a single-arm, open label, phase 2 study testing a fixed dose of cabozantinib combined with the standard-dose immune checkpoint inhibitor pembrolizumab. The study is powered to a primary endpoint of best ORR with the combination of cabozantinib and pembrolizumab. Secondary endpoints include clinical benefit (DCR and duration of DCR), time to response, PFS, and OS. Enrollment for Part 2 will commence only after a RP2D is identified from phase 1.

Treatment will be administered on an outpatient basis. Cabozantinib will be administered orally daily, and pembrolizumab will be intravenous infusion once every 3 weeks. Reported adverse events and potential risks are described in section 2.3. Appropriate dose modifications are described in Section 6.1.2.3. No investigational or commercial cancer directed agents or therapies other than those described below may be administered.

Safety assessment will follow the guidelines provided in the National Cancer Institute Common Terminology Criteria for Adverse Events (NCI-CTCAE) Version 4.03.

Subjects will be followed clinically on the D1 of each cycle and radio-graphically starting 12 weeks after initiation of treatment then every 12 weeks for tumor evaluation. Post-treatment scans will be compared to the baseline scan and responses will be assessed based using RECIST v1.1. Appendix A.

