7.2 PARTICIPANT DISCONTINUATION/WITHDRAWAL FROM THE STUDY

Patients may withdraw from the study at any time. Patients who discontinue early should return within 30 days (+/- 7 days) of the last dose of the study drugs for a follow-up evaluation. Any assessments listed for the final visit in Table will be performed at that time.

In addition, any of the following conditions require the withdrawal of the subject from study treatment:

- An AE or intercurrent illness that in the opinion of the investigator warrants the subject's withdrawal from treatment
 - The investigator believes it is not in the best interest of the subject to continue on study
- Necessity for treatment with other investigational drug or other anticancer medications prohibited by protocol
- Noncompliance with the protocol schedule
- Participation in another clinical study using anticancer agent(s)
- Request by regulatory agencies for termination of treatment of an individual subject or all subjects under this protocol
- Sexually active subjects who refuse to use medically accepted barrier methods of contraception (eg, male condom, female condom) during the course of the study and for 3 months following discontinuation of study treatment
- Women who become pregnant or are breast feeding
- Inability to tolerate cabozantinib
- Cabozantinib treatment delays > 6 weeks unless the subject was unequivocally benefitting from cabozantinib treatment
- Progressive disease (PD) as determined by the investigator. However, patients who continue to derive clinical benefit from cabozantinib and pembrolizumab as judged by the investigator may continue therapy despite radiographic progression of the disease.

The reason for study treatment discontinuation will be documented. For subjects who discontinue or are withdrawn from study treatment, every effort must be made to undertake protocol-specified follow-up procedures and end-of-treatment assessments, if possible, unless consent to participate in the study is also withdrawn.

If a subject fails to return for the protocol-defined visits, an effort must be made to determine the reason. If the subject cannot be reached by telephone, at the minimum a registered letter

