8 STUDY ASSESSMENTS AND PROCEDURES

8.1 EFFICACY ASSESSMENTS

The intention of the study design is to closely monitor patients with safety follow-up and disease assessments in the absence of disease progression or other study discontinuation criteria.

For the purposes of this study, patients should be re-evaluated after the first 12 weeks of treatment and then every 12 weeks. **In addition to a baseline scan, confirmatory scans will** also be obtained at least 4 weeks and no more than 14 weeks following initial documentation of partial or complete response.

Primary efficacy endpoint is best ORR defined as the proportion of all treated subjects whose best response at any time during the study following initiation of therapy is confirmed CR or confirmed PR. This will be assessed according to the RECIST v1.1.(Appendix A).

PFS, defined as the time between the first dose of study therapy and the earliest date of progression or death. Subjects who have neither progressed nor died will be censored at the last tumor assessment date for PFS. The endpoint ORR and PFS will be assessed according to the RECIST v 1.1 criteria.

Additional efficacy endpoints will include the disease control rate (DCR) defined as the percentage of patients achieving CR + PR + SD at any time during the study following initiation of therapy. This will be assessed according to RECIST v1.1 criteria. The duration of response (DOR), is defined as the time between the date that the criteria are first met for CR or PR or SD and the earliest date of progression or death.

OS, defined as the time between the first dose of study therapy and death (subjects who have not died will be censored at the most recent last-known-alive date), will also be analyzed.

The tumor assessment (TA) performed during screening will be used as a baseline for efficacy assessments. CT/MRI imaging of the chest and abdomen is required at Screening and at each TA, regardless of the location of known metastases. In addition, CT/MRI scans must be obtained of anatomic regions not covered by the chest and abdomen scans in subjects where there is clinical suspicion of deep soft tissue metastases (eg, lesions in the thigh). Such additional CT/MRIs will be required at Screening when deep soft tissue disease is known/suspected and must be consistently repeated at all TAs if a deep soft tissue lesion is identified during Screening.

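### Study calendar footnote 16 resets the response baseline to week 12 after tumor growth, against the screening baseline that section 8.1 and Appendix A use for the primary ORR

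*Combined protocol and SAP*

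**What the plan says.** **The reset.** Footnote 16 belongs to the tumor imaging row of the study calendar (section 1.3). It first makes a repeat scan optional after progressive disease (PD), to "exclude the possibility of a tumor flare reaction, according to irRC guidelines", and leaves that scan to the investigator. The next sentence is not optional. Where the week-12 scan shows growth, it orders that "the baseline sum of perpendicular diameters is to be reset to week 12 for subsequent assessment of response". No size of increase is given.

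**The screening baseline.**
- Section 4.1: "Post-treatment scans will be compared to the baseline scan and responses will be assessed based using RECIST v1.1".
- Section 8.1: "The tumor assessment (TA) performed during screening will be used as a baseline for efficacy assessments". Its target-lesion paragraph makes the screening sum the reference for response at every tumor assessment.
- Section 8.1, on the primary endpoint: "This will be assessed according to the RECIST v1.1.(Appendix A").
- Appendix A: PR is a fall of at least 30% in the sum of longest diameters from the baseline sum. PD by target lesions is a rise of at least 20% from the smallest sum. Best response is taken up to progression.
- Section 9.4.2: ORR is the proportion with a RECIST response. The trial stops at 5 or fewer responses in 14 and succeeds at 21 or more in 44.

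**What happens after progression.** Section 1.2 plans "interval imaging every 12 weeks starting from Week 12 until progression with a CT scan and response evaluated per RECIST 1.1". Section 7.2 lets patients judged to benefit stay on: they "may continue therapy despite radiographic progression of the disease". Section 8.1 counts a patient as a responder if the "best response at any time during the study following initiation of therapy is confirmed CR or confirmed PR".

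**The concern.** For a patient whose tumor has grown by week 12, the two rules cannot both be followed. A scorer working from the calendar and a scorer working from section 8.1 can enter PR and stable disease from the same measurements, on the endpoint that decides the trial.

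The discrepancy runs one way. Only patients whose tumors grew get a new reference, and it is always larger than the old one, so PR becomes easier and never harder. The comparison is with a fixed historical 35%, and there is no control arm in which the same leniency would cancel. Because both decisions are fixed counts, one such patient can change either of them.

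**Working it through.** **1. The plan's own design.** Inputs (sections 9.1, 9.2, 9.4.2): null ORR 0.35, alternative 0.55, n1 = 14 with a stop at 5 or fewer, N = 44 with rejection at 21 or more. With X1 and X2 the responses among the first 14 and the next 30 patients:

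P(reject) = sum over x = 6 to 14 of P(X1 = x) × P(X2 ≥ 21 − x)

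- At 0.35: 0.0458
- At 0.55: 0.8001

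The stated alpha of 0.05 and power of 80% reproduce, and a search for the optimal Simon design returns the same boundaries. The design is correct.

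**2. What the reset does to one patient.** Let the week-12 sum be (1 + g) times the screening sum. Apply Appendix A's 30% fall to the reset reference, since the footnote gives no threshold of its own. The PR limit becomes 0.7(1 + g) of the screening sum in place of 0.7, so the extra window is 0.7g wide.

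| Week-12 growth g | PR limit, fraction of screening | Falls from screening newly scored as PR | Width (points) |
|---|---|---|---|
| 5% | 0.735 | 26.5% to 30% | 3.5 |
| 10% | 0.770 | 23% to 30% | 7.0 |
| 15% | 0.805 | 19.5% to 30% | 10.5 |
| approaching 20% | approaching 0.84 | about 16% to 30% | about 14 |

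Example: 100, 118, 82 mm. From week 12, 82/118 = 0.695, a fall of 30.5%: PR if confirmed. From screening, 82/100, a fall of 18%: stable disease. Growth of 18% is under Appendix A's 20% limit, so without new lesions or non-target progression the patient has not progressed and best response is still open.

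**3. Growth of 20% or more.** This is PD under Appendix A. A later reset-based response is then excluded by Appendix A, but it could be counted if the any-time wording of 8.1 is taken alone for a patient kept on therapy under 7.2.

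**4. How often one patient would matter.** Chance of sitting exactly one response short of a boundary:

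| True ORR | Stage 1: P(X1 = 5) | Final: P(X1 ≥ 6 and total = 20) |
|---|---|---|
| 0.35 | 0.218 | 0.031 |
| 0.45 | 0.170 | 0.085 |

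These are properties of the design. They show how sensitive the decisions are to one patient, not how many patients are misclassified.

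**5. Type I error under assumed rates.** The documents give no rate of reset responders. **Assumption, for illustration:** k expected per 44 patients at a true ORR of 0.35, where 44 × 0.65 = 28.6 non-responders are expected.

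- Late model: the stage 1 decision is unaffected. Each non-responder converts with probability (k/44)/0.65 for the final count only.
- Both-stage model: p = 0.35 + k/44 throughout.

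| k (assumed) | k / 28.6 | Late model | Both stages |
|---|---|---|---|
| 0 | 0% | 0.046 | 0.046 |
| 0.1 | 0.3% | 0.048 | 0.049 |
| 0.25 | 0.9% | 0.053 | 0.054 |
| 0.5 | 1.7% | 0.060 | 0.063 |
| 1 | 3.5% | 0.076 | 0.085 |
| 2 | 7.0% | 0.115 | 0.142 |

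**6. Which model is likelier.** After a reset at week 12 the next scheduled scan is at week 24, and confirmation needs at least 4 more weeks: 24 + 4 = week 28 at the earliest. The late model is the more likely one.

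**The case against.** The strongest reply is that the plan already answers the question. Section 8.1 uses the screening sum at every assessment, names RECIST and Appendix A for the primary endpoint, and section 9.4.2 repeats RECIST. Against that stands one calendar footnote. This shows which rule the authors probably meant, and the footnote is best seen as a stray instruction. But these passages are the other side of the conflict. None mentions the reset, and no irRC endpoint exists to which it could belong. Its reference to perpendicular diameters does not set it apart, because 8.1 also defines measurable lesions by two perpendicular diameters.

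The second reply is that the preceding sentence concerns progressive disease and flare, so an increase means apparent progression. With Appendix A closing best response at progression, the ORR is then untouched. This is a reasonable reading and stands as the lower bound, but the sentence sets no threshold and does not say so.

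Four points on size also stand:
- The 118 mm example borrows Appendix A's 30% cut, because the footnote supplies none.
- Section 4.1 says only baseline scan. The word screening comes from 8.1, which carries the argument.
- At 0.1 expected reset responders per 44 the type I error stays below 0.05, so a breach is not inevitable.
- Only some non-responders could convert. If 20% of them had the qualifying growth (an assumption), k = 2 would need 35% of those to convert (7.0%/20%), so the upper rows are demanding.

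**Conclusion.** The concern holds. Footnote 16 gives a mandatory rule on the primary endpoint that contradicts section 8.1 and Appendix A, and following it gives a wrong response classification. It should be fixed.

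On the literal reading, week-12 growth above 0% and below 20% lets a fall from screening of between about 16% and 30% be scored as PR. The bias is upward only. Its effect on the trial cannot be computed from the documents. It is nil if the footnote means progression only and Appendix A closes best response. On the assumed rates of 0.5 to 2 reset responders per 44, the type I error is 0.060 to 0.115 in the likelier late case and 0.063 to 0.142 if they count at both stages. The Simon design itself is not in question, and nothing here shows that any patient has been misclassified.

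**What to change.** - Delete the reset sentence from footnote 16, or limit it to a labelled exploratory analysis that does not feed the primary ORR or the stage 1 and final counts.
- In section 8.1, state that PR for the primary ORR is judged against the screening sum of target-lesion diameters, that complete response is disappearance of lesions as Appendix A defines it, and that best response closes at RECIST progression as Appendix A says. The last clause is needed because the any-time wording in 8.1 otherwise leaves the post-progression route open.
- Re-score, from the recorded measurements, any patient already assessed against a reset baseline.

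The cost is one sentence removed or relabelled and a short clarification in 8.1. Boundaries, sample size and treatment do not change. The reported ORR may be slightly lower.
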